8.4 Rationale for Study Endpoints

Each of the primary and secondary safety and/or efficacy endpoints above aligns with the primary objective of the study in evaluating acute safety and efficacy of the S.M.A.R.T. RADIANT™ Vascular Stent System,

RADIANT / P21-7701

Version: 7.0 / March 21, 2023

when used with the BRITE TIP RADIANT™ Guiding Sheath and SABERX RADIANT™ PTA Balloon Catheter in treating femoropoliteal or iliac artery lesions via a radial artery approach.

Regarding the S.M.A.R.T. RADIANT device in particular: since the investigational S.M.A.R.T. RADIANT delivery system incorporates the CE marked S.M.A.R.T. stent, for which there is an abundance of short-term and long-term clinical data available from its evaluation in previous, Cordis-sponsored studies, the main purpose of this study is to assess the safety and performance (outcomes) of the delivery system versus the stent. There is proven, long-term primary patency through 10 years and low stent fracture rate through 3 years following implantation of the S.M.A.R.T. stent. Therefore, rates of vessel patency, restenosis, stent fractures, etc. have not been included as pre-specified endpoints for this study.

The various health economic endpoints will be used to determine if there are cost savings/benefits, such as decreased procedural/treatment and hospitalization costs, for patients who are eligible for and undergo procedures that can be completed via a transradial versus transfemoral arterial approach. General and disease-specific outcomes assessed via the SF-36 and EQ-5D standarized, validated questionnaires will help determine if there is overall, improved quality-of-life in the short-term in patients that undergo stenting procedures via transradial approach to 30 days post-procedure.

9 Informed Consent

Prior to enrollment and performance of any study-specific activities or procedures, the study team shall:

1. Provide each prospective subject with a full explanation of the study (including all potential benefits and risks) that is also documented (i.e., informed consent form) and ensure they have understood all information that has been presented to them.
 - a. The informed consent form (ICF) should enable the subject to understand:
 - i. the nature, objectives, benefits, implications, risks and inconveniences of the clinical investigation;
 - ii. the subject's rights and guarantees regarding his/her protection, in particular his/her right to refuse to participate in and the right to withdraw from the clinical investigation at any time without any resulting detriment and without having to provide any justification;
 - iii. the conditions under which the clinical investigations are to be conducted, including the expected duration of the subject's participation in the clinical investigation; and
 - iv. the possible treatment alternatives, including the follow-up measures if the participation of the subject in the clinical investigation is discontinued.
 - b. The ICF shall:
 - i. Be comprehensive, concise, clear, relevant and understandable to the subject;
 - ii. Be provided in a prior interview with a member of the clinical investigation team who is appropriately qualified under national law and delegated to this responsibility; gives special attention to the information needs of specific patient populations and individual subjects as well as to the methods used to provide the information; verifies the subject has understood the information;
 - iii. Include information about an applicable damage compensation system; and
 - iv. Include the unique, study identification number and information about the availability of clinical study results to the subject, to the extent possible, via a clinical study report and summary presented in terms understandable to the intended user, irrespective of the outcome of the clinical study.
2. Allow adequate time for the prospective subject to read the most current EC-approved informed consent form (ICF) and consider participation in the study and for addressing any/all of their questions.

RADIANT / P21-7701

Version: 7.0 / March 21, 2023

Cordis[®]

3. Obtain documented consent [handwritten or electronic (if applicable) signature and date on the ICF] from the prospective subject after it is certain they understand all implications of participating in the study. The ICF shall also be signed by the Investigator or person performing the interview. Alternatively, in situations where the subject is unable to write, consent may be provided in the presence of at least one impartial witness, who shall sign and date the ICF.

The reflection period (time between explaining the study/providing written information to the prospective subject and obtaining documented consent) can vary based on individual circumstances, but should be at least 24 hours in duration or per standard practice or institutional policies at each site.

A copy of the ICF (or other record by which informed consent had been provided) that is signed by the subject and the Investigator and/or designee obtaining consent will be provided to the subject.

The Investigator and/or designee must clearly document the process for obtaining informed consent, including the date and time of obtaining consent, in the subject's medical record. It is the Investigator's responsibility to ensure that the informed consent process is performed in accordance with ICH-GCP applicable international standards and all applicable local and federal regulations.

Documented informed consent must be obtained within 60 days prior to the index procedure.

Exceptions to obtaining documented informed consent prior to the initiation of study-specific procedures would be in cases where necessary to eliminate an immediate apparent hazard and protect the life or physical well-being of a study subject, as determined by the investigator. See section 15.5.3 (Emergency Deviations). In such cases, informed consent must be obtained from the subject following the same process as described above as soon as possible following the index procedure.

10 Screening and Enrollment

10.1 Overall Process

The sequence of steps in the evaluation of potential patients for study enrollment is described as follows and diagrammed in **Figure 1**. Refer to **Section 7** for a list of all inclusion and exclusion criteria.

1. **Pre-Screening:** The potential patient will be evaluated against all inclusion and exclusion criteria that can be assessed via review of their medical records.
2. **Informed Consent:** A patient who is shown to qualify for the study based on medical record review alone will be asked to provide documented informed consent to participate in the study as described in **Section 9**.
3. **Screening:** A patient who provides informed consent will be evaluated against all other inclusion and exclusion criteria via study-specific assessments performed through the time of index procedure (i.e., angiography).
4. **Enrollment:** A patient who meets all criteria as outlined in **Section 10.3** can be enrolled into the study.

Figure 1: Patient Evaluation Process

RADIANT / P21-7701

Version: 7.0 / March 21, 2023

10.2 Pre-Screening and Screening

10.2.1 Data Collection and Assessments

In addition to obtaining documented informed consent within 60 days prior to the index procedure, the following must be (except as indicated below) performed or obtained. Subjects will be verified to meet all inclusion criteria and none of the exclusion criteria prior to device implantation.

1. **Demographic Data:** Including but not limited to age, sex, weight, height, and race
2. **Medical/Surgical History:** Including but not limited to vascular and non-vascular clinical history, risk factors, medical and surgical cardiovascular background (i.e., history of cardiac, kidney or peripheral vascular disease, diabetes, hypertension, bleeding history, hypercholesterolemia, TIA, stroke, renal insufficiency, allergies, tobacco use)
3. **Physical Examination:** Complete review of systems must be completed within seven (7) days prior to the day of the index procedure
4. **Concomitant Medications (recommended):** Aspirin AND either Clopidogrel bisulfate (Plavix®) or Ticlopidine (Ticlid®). Please see **section 11.5**.
5. **Laboratory Evaluations:** Non-fasting results are acceptable. The patient should be adequately hydrated prior to obtaining laboratory tests. The following tests must be completed within seven (7) days prior to the day of the index procedure.
 - a. Glomerular filtration rate assessment
 - b. Pregnancy test (if the patient is female and of child-bearing potential)
6. **Duplex Ultrasound:** This must be completed of the radial artery that will be used as the access site within seven (7) days prior to the day of the index procedure. Refer to the Core Lab reference manual for guidelines on performing and submitting this assessment.
7. **Health-Related Quality of Life:** Assessed via the SF-36 and EQ-5D questionnaires that are completed by the subject or administered to the subject by a study team member at the site (if possible) within seven (7) days prior to the day of the index procedure.
8. **Baseline Angiography:** Performed at the time of index procedure

The baseline angiography (assessment 8) will be done at the time of the index procedure. The site's visual assessment from the baseline angiography will be used to determine the subject's eligibility for the study according to all anatomically-related inclusion/exclusion criteria, however, all angiograms will also be sent to the core lab for further analysis.

10.2.2 Screen Failures & Pre-Screen Failures

Pre-screen Failures: Pre-screen failures are defined as patients who are confirmed to not qualify for study participation according to the eligibility criteria after review of their medical records (i.e., prior to providing informed consent). Such subjects will neither be treated with the study devices nor followed per protocol.

RADIANT / P21-7701

Version: 7.0 / March 21, 2023

Screen Failures: Any consented patient who is confirmed to not qualify for study participation according to the eligibility criteria will be considered a screen failure and will neither be treated with the study devices nor followed per protocol.

Signed informed consent forms and all applicable documentation including source records indicating rationale for screen failure classification and Screening/Enrollment logs or equivalent forms/screens in the Electronic Data Capture (EDC) system will be reviewed during monitoring visits for all screen failure patients.

10.2.3 Duration

The screening of potential patients for this study is anticipated to occur over a 4-6 month period.

10.3 Enrollment

The subject will be considered enrolled into the study after ALL of the following criteria have been met:

- ICF has been signed/dated by all parties
- All pre-screening and screening assessments have been completed
- Vascular access has been obtained in the radial artery (i.e., time of puncture)
- Subject has been assessed by the site against all study eligibility criteria, including those determined by angiography

11 Treatment Plan

11.1 Index Procedure

The Instructions for Use (IFU) provides detailed information on the product, safety, storage, design, deliverability, and sizing specifications for all three (3) devices: S.M.A.R.T. RADIANT, BRITETIP RADIANT and SABERX RADIANT. All information within the IFU for each device should be reviewed prior to initiation of the index procedure and implantation of the study stent.

NOTE: Left side radial artery access is recommended/preferred for all subjects.

NOTE: There is currently no data available to support use of the study devices via the distal radial artery as the access site.

CAUTION: The height of each subject must be considered to ensure the S.M.A.R.T. RADIANT delivery system is adequate in length to be tracked to the site of the target lesion.

1. Initial Angioplasty using SABERX RADIANT PTA Balloon Catheter (if appropriate)

- a. An angioplasty balloon catheter should be selected to correspond to the diameter of the superficial femoral artery proximal to the lesion. The side arm of the introducer should be connected to a pressure transducer to record the arterial pressure distal to the obstruction. An initial dilation of the lesion should be made with an appropriately sized balloon catheter. Whenever there is doubt about the dispensability of the lesion, the smallest appropriate balloon catheter should be used for the initial dilatation.

Note: Stent placement is not indicated if the primary angioplasty is not technically successful. A technically successful angioplasty is one in which the guidewire and dilation catheter are passed through the lesion and dilatation of the lesion produces a lumen adequate to accommodate introduction of the stent delivery system.

RADIANT / P21-7701

Version: 7.0 / March 21, 2023

- b. Following dilatation of the lesion, an arteriographic image should be recorded in order to determine the adequacy of the primary procedure.
- 2. Select S.M.A.R.T. Stent Size**
 - a. Measure the length of the target lesion to determine the length of stent(s) required, as per Table 3. Size the stent length(s) to extend slightly proximal and distal to the lesion.
 - b. The appropriate stent length(s) should be selected to cover the entire length of the lesion.
 - c. The appropriate unconstrained stent diameter should be selected based on the vessel lumen diameter as per Table 6.

Table 6: Stent Size Selection Guide

Vessel Lumen Diameter	Unconstrained Stent Diameter
4.0 – 5.0 mm	6 mm
5.0 – 6.0 mm	7 mm
6.0 – 7.0 mm	8 mm
7.0 – 8.0 mm	9 mm
8.0 – 9.0 mm	10 mm

Note: Refer to product labeling for stent length information

- 3. Insertion of BRITE TIP RADIANT Guiding Sheath or Guide Catheter and Guidewire**
 - a. Access the treatment site utilizing the appropriate accessory equipment compatible with the 6F (2.0 mm) delivery system.
 - b. Place a 6F guiding sheath of an appropriate length (110cm for a 150cm long delivery system and a 135cm for a 190cm long delivery system) with an internal diameter of at least 2.2 mm.
 - c. Place an .018" (0.46 mm) guidewire of sufficient length across the lesion to be stented via the guiding sheath or guide catheter.
- 4. Dilation of Lesion with SABERX RADIANT PTA Balloon Catheter (if appropriate)**
 - a. Pre-dilate the lesion using standard PTA balloon catheter techniques.
 - b. Remove the PTA balloon catheter from the patient while maintaining lesion access with the guidewire.
- 5. Stent Deployment**
 - a. Verify that the delivery system's radiopaque stent markers (leading and trailing ends) are proximal and distal to the target lesion.

RADIANT / P21-7701

Version: 7.0 / March 21, 2023

- b. Initiate stent deployment by rotating the thumbwheel in a clockwise direction while holding the handle in a fixed position.
- c. While using fluoroscopy, maintain position of the radiopaque stent markers relative to the target lesion site. Watch for the distal radiopaque markers to begin separating. Separation of the distal stent markers signals that the stent is deploying. Continue turning the tuning dial to cause further separation of the distal radiopaque markers until the distal end of the stent obtains full wall apposition.
- d. Deployment is complete when the proximal markers oppose the vessel wall and the outer sheath radiopaque marker is proximal to the support member stent stop.

6. Post-deployment Stent Dilatation with SABERX RADIANT PTA Balloon Catheter (if appropriate)

- a. While using fluoroscopy, withdraw the entire delivery system as one unit, over the guidewire, into the guiding sheath and out of the body. Remove the delivery device from the guidewire. Do not rotate the handle during withdrawal.
- b. Using fluoroscopy, visualize the stent to verify full deployment. Post-deployment balloon dilatation can be performed within the stent at any point along the lesion where there was incomplete expansion.
- c. Select an appropriate size PTA balloon catheter, dilate the lesion with conventional technique and remove the PTA balloon from the patient.

7. Post Stent Placement

- a. Remove the guidewire and sheath from the body.
- b. Close entry wound as appropriate.

NOTE: It is required to use S.M.A.R.T. RADIANT as the stent delivery system, BRITE TIP RADIANT as the guiding sheath and SABERX RADIANT as the PTA balloon catheter (if pre-dilation and/or post-dilatation is performed) during the index procedure to be able to adequately evaluate the performance of all three (3) devices.

Though subjects are considered enrolled only from the time they are confirmed to qualify for study participation according to the eligibility criteria (i.e., upon completion of angiography), all events for enrolled subjects, which include all adverse events and device deficiencies, will be reported retroactive to when vascular access was established in the radial artery (i.e., time of puncture), in the case of adverse events, or initial use or handling of a study device, in the case of device deficiencies.

11.2 Treatment of Bilateral Stenosis

A patient with bilateral stenosis (lesions in both limbs) can have both lesions treated without a waiting period (e.g., during the index procedure). In all cases, a lesion on the second/contralateral limb can **ONLY** be treated with the study devices, via transradial approach and if it meets all applicable study eligibility criteria.

11.3 Treatment Failures

In the event of a device deficiency, detailed information on the product, circumstances of the deficiency as well as any complications and their management will be collected and reported to the sponsor, as described in Section 13.6.

RADIANT / P21-7701

Version: 7.0 / March 21, 2023

Failure to implant the assigned study device will be recorded on the CRF as a treatment failure. In the event of a treatment failure, each site will follow their standard-of-care procedures (and/or use commercially-available products) to ensure the safety of the subject.

Any subject enrolled in this clinical study that does not receive the study device (S.M.A.R.T. stent) will be followed to 30 days post-procedure to be monitored for safety (adverse events and overall health) but will not be required to complete any of the study-specific procedures/assessments scheduled for the 30-day follow-up visit. If applicable, the Investigator must return any malfunctioned/damaged/unused investigational devices to the sponsor or its designee in accordance with the instructions provided.

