8.3 Additional Data Points

Data will be collected to evaluate the following health economics outcomes:

- Fluoroscopy time and procedural time, defined as the time of sheath introduction to time of vascular closure.
- Time to achieve hemostasis,
- defined as the time elapsed from removal of the BRITE TIP RADIANT™ Guiding Sheath to the time that hemostasis was first observed. Time to ambulation, defined as when the subject can stand up and walk any distance
- Time to hospital discharge
 - Time to hospital discharge eligibility (when physician examines and if all is well, gives discharge orders).

Method to achieve closure of the transradial artery access site

Quality of Life Assessments: Data will be also collected to evaluate health-related, quality-of-life in all subjects by administering the 36-item Short Form Health Survey (SF-36) and the EuroQOL-5 Dimension (EQ-5D) standardized, validated questionnaires to assess general and disease-specific outcomes. Brief descriptions of these two questionnaires are as follows

- The SF-36 is a patient-reported survey of general health and well-being. It consists of 36 items grouped in these dimensions: physical functioning, physical and emotional limitations, social functioning, bodily pain, general and mental health. Higher scores indicate better health status.
- The EQ-5D questionnaire is used for the assessment of health state utility and visual analog rating, which is a quantitative measure of overall health status. It consists of five (5) dimensions: mobility, self-care, usual activities, pain/discomfort and anxiety/depression.

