11.4 Post-Procedure Care/Discharge (+7 days)

Following the index procedure, the site will notify the sponsor of the subject enrollment status (i.e., whether the subject was enrolled or was a screen failure).

In addition to the standard-of-care procedures at each participating site, all subjects will undergo these assessments at time of discharge (+ 7 days):

1. Concomitant Medications (recommended):

Post Procedure: Clopidogrel bisulfate (Plavix®) – 75 mg qd
or
Ticlopidine (Ticlid®) – 250 mg b.i.d.

After Discharge: Aspirin – 75-325 mg qd indefinitely
Clopidogrel bisulfate (Plavix®) – 75 mg qd for at least 30 days

or
Ticlopidine (Ticlid®) – 250 mg b.i.d. for at least 30 days

2. Adverse Event Monitoring

3. Quality of Life Assessment: SF-36 & EQ-5D

4. Duplex Ultrasound*: This must be completed of the radial artery that was used as the access site during the index procedure. Refer to the Core Lab reference manual for guidelines on performing and submitting this assessment.

If a hospital's standard-of-care requires additional imaging assessments prior to discharge that are not required per the study protocol, copies should be sent to the Core Lab.

Upon discharge, subjects must be given a Stent Implant Card with specific "MR Conditional" information included.

* Post-procedure duplex ultrasound can be completed any time between discharge and the 30-day follow-up visit per standard practice. If not standard-of-care at the site, this assessment must be completed at discharge.

RADIANT / P21-7701

Version: 7.0 / March 21, 2023

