14.1 Analysis Population

Analyses for the endpoints will be performed using the intent-to-treat (ITT) population. The ITT population will consist of all subjects enrolled in the study and for whom a device insertion was attempted, regardless of the treatment actually received.

RADIANT / P21-7701

Version: 7.0 / March 21, 2023

The per-protocol analysis population is defined as a sub-group of the ITT population consisting of subjects without protocol deviations that could possibly affect the primary endpoints. Primary endpoint analysis using this population is supportive in nature.

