**6 ANALYSIS POPULATION**

Analyses for the endpoints will be performed using the intent-to-treat (ITT) population. The ITT population will consist of all subjects enrolled in the study, excluding roll-ins, and for whom a device insertion was attempted, regardless of the treatment actually received.

The per-protocol analysis population is defined as a sub-group of the ITT population consisting of subjects without protocol deviations that could possibly affect the primary endpoints. Primary endpoint analysis using this population is supportive in nature.

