## 8.7 Additional Endpoints

The additional data points of fluoroscopy time, procedural time, time to achieve hemostasis, time to ambulation, time to hospital discharge, time to hospital discharge eligibility, method to achieve closure, and the scoring of the EQ-5D and SF-36 will be completed on a per subject basis.

Estimates of each of the endpoints related to time will be summarized with a mean, standard deviation, median, and a range expressed as a minimum and maximum. For each estimate, a two-sided 95% confidence interval will be calculated using normal approximation methods.

The method of vascular closure will be reported as the percent of subjects falling into closure categories.

The EQ-5D will be reported as the proportion of subjects falling within the scale for each domain at three time points; Screening, Discharge, and 30 day follow-up. Each domain is a rank-order scale in which lower numbers represent outcomes superior to those represented by higher numbers (i.e. "1" is best and "5" is worst) for each time point. Overall health score, however, is reported as a mean and standard deviation at each time point. For the SF-36, results within each subscale will be summarized with a mean and standard deviation at three time points: screening, discharge and 30-day follow-up.

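### Protocol 11.3 waives the 30-day quality-of-life assessments for subjects without the stent, although quality of life is planned in all subjects and summarised at 30 days without restriction

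*Protocol*

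**What the plan says.** **The waiver.** Protocol 11.3 classes failure to implant the study device as a treatment failure. Safety follow-up of an enrolled subject without the stent continues to day 30 and covers adverse events and general health. Such a subject, however, "will not be required to complete any of the study-specific procedures/assessments scheduled for the 30-day follow-up visit".

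**Quality of life.** Protocol 8.3 states: "Data will be also collected to evaluate health-related, quality-of-life in all subjects". Table 1 marks SF-36 and EQ-5D at screening, discharge and 30 days with no exception, and Protocol 11.6 lists them among the 30-day assessments. For the SF-36, SAP 8.7 says that "results within each subscale will be summarized with a mean and standard deviation at three time points". EQ-5D is reported at the same three points. Neither document restricts these summaries to implanted subjects.

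**Analysis set.** The endpoint analyses use the ITT set. SAP 6 defines it as enrolled subjects, "excluding roll-ins, and for whom a device insertion was attempted, regardless of the treatment actually received".

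**Radial duplex.** Protocol 11.4 lists the scan among the discharge assessments for all subjects. Its footnote adds: "Post-procedure duplex ultrasound can be completed any time between discharge and the 30-day follow-up visit per standard practice". Sites where the scan is not standard of care must do it at discharge. Table 1 places the scan in the 30-day column with the same footnote. Protocol 11.6 does not list it and refers back to 11.4.

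**Missing data.** Protocol 14.5 and SAP 11 plan worst-case imputation for the two primary endpoints. Protocol 14.5 plans none for secondary endpoints. Nothing is said about the quality-of-life data, which are additional data points.

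**The concern.** The result of the procedure decides who is measured at 30 days. A subject in whom the stent could not be placed completes the questionnaires at screening and discharge but need not complete them at day 30. The three summaries in SAP 8.7 would be read side by side as a course over time. The third can come from a subset from which treatment failures have been removed because they failed. If those subjects feel worse at day 30, the 30-day figures look better than they should, and nothing requires the report to show that the denominator changed for this reason.

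The same wording leaves a smaller doubt about the post-procedure radial scan. A site that scans at the 30-day visit could read 11.3 as excusing non-implanted subjects from it. Protocol 14 says the study is about access and delivery, so these subjects are informative for that question.

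**Working it through.** **1. The plan's own figure.** Inputs (Protocol 14.3, SAP 5): n = 129, assumed success 98%, goal 93%, one-sided exact 95% bound.
- Efficacy: the smallest number of successes whose Clopper-Pearson lower bound exceeds 93% is 125 of 129 (bound 93.05%). Type I error is 0.0481 and power is 0.882.
- Safety: the largest number of events whose upper bound is below 7% is 4 of 129 (bound 6.95%). Type I error is 0.0481 and power at a 2% rate is 0.882.

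Both match the stated 88%.

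**2. Do the waived assessments feed a primary endpoint?** Technical success is settled at the end of the index procedure (Protocol 8.1.2). The primary safety window closes at hospital discharge (8.1.1). The waiver covers only assessments scheduled for the 30-day visit. Neither endpoint uses them, so n and power stay as they are.

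**3. How many subjects?** Expected number = n × (1 − p), with p the technical success rate. This assumes one limb per subject and counts every technical failure as a non-implant. The second assumption makes it an upper bound, because a failure with a stent in place is not exempt.

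| Technical success | Expected non-implants | 95% range |
|---|---|---|
| 98% | 129 × 0.02 = 2.6 | 0 to 6 |
| 93% | 129 × 0.07 = 9.0 | 4 to 15 |

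At 98% the chance of at least one is 1 − 0.98^129 = 0.93. If the efficacy goal is met on 129 limbs, there are at most 129 − 125 = 4 failures.

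**4. How far can a 30-day mean move?** Let f be the non-implanted share and D the mean in implanted subjects minus the mean in non-implanted subjects. The full mean is (1 − f) × implanted mean + f × non-implanted mean. Leaving the non-implanted out therefore shifts the mean by f × D. The documents give no value for D; 5 to 20 points is an assumed range.

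| f | D = 5 | D = 10 | D = 20 |
|---|---|---|---|
| 2% | 0.1 | 0.2 | 0.4 |
| 4/129 = 3.1% | 0.16 | 0.31 | 0.62 |
| 7% | 0.35 | 0.7 | 1.4 |

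**5. Does the waiver reach the duplex?**
- At sites where the scan is not standard of care, it is due at discharge and lies outside the waiver.
- At sites that scan later, 11.4 (all subjects) and 11.6 (scan not listed) suggest that it is still due. The 30-day column of Table 1 suggests that it could be waived.

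The texts do not settle the second case.

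**The case against.** The strongest reply is that the waiver fits the stated purpose. Protocol 8.4 says the questionnaires help to judge "improved quality-of-life in the short-term in patients that undergo stenting procedures via transradial approach to 30 days post-procedure". A subject who never received the stent and was then managed by local standard of care is arguably outside that question. SF-36 and EQ-5D are also additional data points rather than endpoints, their rows in SAP Table 1 are marked for the non-roll-in and roll-in cohorts rather than ITT, and they are descriptive. All of this stands, and it limits the weight of the point. It does not remove the conflict: no analysis set is restricted to match that purpose, and Protocol 8.3 says all subjects.

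A reader might also infer more than the documents support:
- **That these subjects leave follow-up.** They do not. Safety follow-up to day 30 is kept, so the 30-day rates of adverse events, death, amputation and revascularisation remain covered. Quality of life at discharge is still required, and an assessment that is not required may still be done.
- **That data are lost in every failure.** Only subjects without the stent are exempt. A technical failure with a stent in place, such as one at the wrong location or with a withdrawal problem, keeps every 30-day assessment.
- **That every exempt subject is in the ITT set.** Membership needs an attempted device insertion and excludes roll-ins.
- **That a lost scan could alter the safety rate tested against 7%.** That window closes at discharge, before the waiver takes effect, and no endpoint is defined by duplex.
- **That non-implanted subjects are especially prone to access-artery injury.** Neither document gives such a rate, and failure to implant may equally reflect a lesion or delivery problem.

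**Conclusion.** The point holds as an inconsistency with a small consequence. Protocol 11.3 makes 30-day quality-of-life measurement depend on the outcome of the procedure. This conflicts with Protocol 8.3, 11.6 and Table 1, and SAP 8.7 has no rule for the resulting gap. For the radial duplex the matter is unclear only at sites that scan after discharge.

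The expected number affected is at most about 2.6 of 129 at 98% technical success and 9.0 at 93%, given one limb per subject and every failure a non-implant. The shift in a 30-day mean is about 0.1 to 0.4 points at 2% and 0.35 to 1.4 points at 7%, resting wholly on the assumed difference of 5 to 20 points. The direction is favourable only if non-implanted subjects do worse, which is plausible but not documented. No primary endpoint, power figure or decision rule changes. This is a cheap improvement, not a threat to the trial's conclusions.

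**What to change.** - In Protocol 11.3, remove the waiver for SF-36 and EQ-5D.
- In the same section, state that the single post-procedure radial duplex required of all subjects in 11.4 also applies to subjects without the stent, and bring Table 1, 11.4 and 11.6 into line.
- In SAP 8.7, report 30-day quality-of-life completion by implant status.

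If the sponsor prefers to keep the waiver, the lesser alternative is to say in Protocol 8.3 and SAP 8.7 that the 30-day quality-of-life summary is restricted to implanted subjects, and to report the number missing by implant status.

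The cost is a wording change and two questionnaires in a few subjects who are already followed to day 30. At late-scanning sites it adds one scan that is already scheduled for everyone else. The sample size does not change.
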